13.2.3. Parts 1 and 2 Biomarkers

To determine the frequency of CTC and molecular alterations in CTCs, whole blood will be collected before, during, and after treatment for CTC enumeration and molecular characterization of a panel of markers including AR-V7.

Serum will be collected from all patients before, during, and after therapy and analyzed for total testosterone, free testosterone, dihydrotestosterone (DHT), estradiol, dehydroepiandrosterone sulfate (DHEA-S), androstenedione, and sex hormone-binding globulin (SHBG) and analyzed locally.

13.3. Archival Tumor Specimens

Archival specimens (formalin-fixed, paraffin-embedded) of the primary cancer and/or metastatic cancer specimen for each study participant will be obtained, if they are available, to evaluate primary response and high-risk markers, including but not limited to TMPRSS2-ERG, PTEN, FGFR, PI3K, BRACA1, BRCA2, and ATM. It is preferable that the entire paraffin block be submitted, but if this is not feasible, then at least 10 unstained slides are requested for immunohistochemical analysis (sections of ~5 microns are preferred). Samples will be stored at room temperature and shipped to a third party laboratory for storage until the time of analysis. See separate laboratory guide for further collection and shipment information.

13.4. Sample Collection and Handling

The actual dates and times of sample collection must be recorded in the eCRF or laboratory requisition form.

Refer to the Schedules of Assessments ([Table 7](#) and [Table 8](#)) for the timing and frequency of all sample collections.

Instructions for the collection, handling, storage, and shipment of samples are found in the laboratory manual that will be provided. Collection, handling, storage, and shipment of samples must be under the specified, and where applicable, controlled temperature conditions as indicated in the laboratory manual.

14. STATISTICAL METHODS

Statistical analysis will be done by the sponsor or under the authority of the sponsor. A general description of the statistical methods to be used to analyze the efficacy and safety data is outlined below. Specific details will be provided in the Statistical Analysis Plan.

No formal hypothesis testing will be conducted. Data will be summarized using descriptive statistics. Continuous variables will be summarized using the number of observations, mean, standard deviation, coefficient of variation, median, and range as appropriate. Categorical values will be summarized using the number of observations and percentages as appropriate. Time-to-event endpoints will be summarized using Kaplan-Meier estimates.

14.1. Analysis Populations

The analysis populations are as follows:

- **Safety population:** This population includes all patients who received at least 1 dose of study drug.
- **DLT evaluable analysis set:** This set is a subset of the safety population. Patients who receive $\geq 75\%$ of planned doses of TRC253 or who had a DLT during the DLT evaluation period will be included in this analysis.
- **PK analysis set:** This set consists of all patients who receive at least 1 dose of study drug and have at least 1 post dose concentration measurement of TRC253. This group will be used for summaries (tables and listings) and listings of derived PK parameters. Note: patients will be removed from the estimation of certain PK parameters on an individual basis due to, for example, missing PK samples such that the PK parameters cannot be appropriately derived. These patients will be identified at the time of the analyses along with their reason for removal.
- **Efficacy analysis set:** This population includes all patients who received at least 1 dose of study drug and underwent a relevant efficacy assessment.

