Blood pharmacokinetic sampling	Plasma samples will be obtained pre-dose. On cycle 1 day 15, samples will be obtained pre-dose and 6 hours post-dose (+/- 15 min).			X	X	X (Pre-dose and 6 hours post-dose)	X	X	X	X
Biomarkers										
AR mutation testing	See lab manual for further instructions.	X						X (Cycle 5 only)	X	
CTC collection	Enumeration and molecular profiling. See lab manual for further instructions.			X				X (Every 3 cycles: C4, C7, etc.)	X	
Testosterone, free testosterone, DHT, estradiol, DHEA-S, androstenedione, and SHBG	The appropriate amount of serum should be drawn to be analyzed locally.		X (Testosterone only)	X				X (Every 3 cycles: C4, C7, etc.)	X	
Archival Tumor Tissue	If available		(X)							
Disease evaluations										
Serum PSA			X	X				X	X	
CT or MRI scan of the chest and abdomen/pelvis	EOT assessments do not need to be repeated if they were performed within 28 days while on treatment.		X					X (C3, then every 3 cycles: C6, C9, etc.)	X	
Radionuclide bone scan			X					X (C3, then every 3	X	

Study Procedures	Notes	Pre-Screening	Screening	Cycle 1 (28 days)				Cycles 2+ (28 days)	End of Treatment	Follow-Up (EOT+28 days)
			Day -28	Day 1	Day 8	Day 15	Day 22	Day 1		
								cycles: C6, C9, etc.)		
Ongoing review										
Concomitant therapy		Continuous from signing of informed consent through 28 days after EOT visit.								
Toxicity assessment/adverse events										

The allowable window for each visit within the cycle is ± 2 days unless otherwise stated.

The allowable window for Follow-Up visit and all scans is ± 7 days.

(X) for an assessment at the Follow-Up (EOT+28 days) visit indicates the assessment does not need to be performed if there were no abnormalities observed for the assessment at the End of Treatment visit.

Safety assessments (except for ECG) on C1D1 do not need to be repeated if they were completed within 7 days prior in screening.

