7.4.3. Patient Withdrawal Criteria

A patient will be withdrawn from the study for any of the following reasons:

1. Lost to follow-up or noncompliant

2. Withdrawal of consent
3. The sponsor terminates the study
4. Disease progression according to PCWG3 criteria ([Appendix 2](#), [Appendix 3](#))
 - a. Patients may continue on study drug if in the opinion of the Investigator, patient is deriving benefit from continuation of therapy. Continuation of therapy must be approved by the Sponsor.
5. Dose delay greater than 21 days
Note: In part 1, only patients who have received >75% of TRC253 doses during the DLT evaluation period will be considered evaluable. Patients who have received \leq 75% of TRC253 doses during the DLT evaluation period due to reasons other than toxicities, such as but not restricted to disease progression, missed appointments, non-compliance, and patient withdrawal, will be considered non-evaluable for DLT and will be replaced with a new patient.
6. Patients with AST or ALT elevations >5X ULN, or who meet Hy's Law criteria, i.e., concurrent elevation of AST or ALT >3X ULN and total bilirubin >2X ULN
7. Grade 4 adverse events
8. Patients who experience QTcF prolongation > 500 ms or > 60 ms change from baseline without electrolyte abnormalities and without response to TRC253 (See [Section 8.5.3](#))

If a patient discontinues study drug and withdraws from the study, the off-study visit assessments should be obtained.

If a patient is lost to follow-up, every reasonable effort must be made by the study-site personnel to contact the patient and determine the reason for discontinuation/withdrawal. The measures taken to follow up must be documented.

Study drug assigned to the withdrawn patient may not be assigned to another patient. Patients who withdraw for reasons other than toxicity will be replaced at the discretion of the sponsor.

If the patient withdraws consent, no further evaluation should be performed and no further attempt should be made to collect additional data. Data and samples that have already been collected will still be used as outlined in this study.

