14.2. Sample Size Determination

The sample size for this study is not calculated based on statistical power but to obtain safety, PK, and PD assessments of oral doses of TRC253. In Part 1, dose escalation, patients up to six patients per dose level will be enrolled to evaluate for DLT. In Part 2, dose expansion, approximately 60 patients will be enrolled into three separate cohorts for further safety and PK evaluation. For example, if true PSA response rate is 50%, the probability of observing at least 11 responders out of 30 in cohort 2 is 95%. If the total of 30 patients from this example, if 15 are PSA responders, then response rate (95% CI) will be 50% (31.3%, 68.7%).

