14.3. Endpoint Definitions

PSA Response at Week 12

PSA response is defined as a $\geq 50\%$ decline from baseline according to PCWG3 criteria ([Appendix 2](#)). An additional PSA obtained at least 4 weeks later must show $\geq 50\%$ decline from baseline to confirm the response.

Time to PSA Progression

Time to PSA progression is measured from the start of treatment until the criteria for PSA progression according to the PCWG3 are met ([Appendix 2](#)). Patient without PSA progression will be censored at the last PSA assessment.

Radiographic Progression-Free Survival (rPFS)

Radiographic Progression-Free Survival (rPFS) is measured from the start of the treatment until the criteria for radiographic disease progression are met or death occurs, whichever is first. Patient will be censored at the last disease assessment when no rPFS event is observed.

Pharmacokinetic Parameters

Pharmacokinetic parameters of TRC253 will be derived from plasma concentration versus time data after single dose and repeat dose, as applicable. The pharmacokinetic parameters to be assessed are shown below. Other parameters may also be assessed.

C_{max}	Maximum observed plasma concentration for each patient
C_{min}	Observed plasma concentration at the end of dosing interval for each patient
t_{max}	Time of maximum observed plasma concentration
AUC_{τ}	Area under the plasma concentration-time curve from time zero to 24 hours (dosing interval) at steady state
AUC_{last}	Area under the plasma concentration-time curve from time zero to the last time measured
AUC_{∞}	Area under the plasma concentration-time curve from time zero extrapolated to infinite time calculated as $AUC_{last} + C_{last}/\lambda_z$, where C_{last} is the last observed measurable (non-BQL) concentration; extrapolations of more than 20.00% of the total AUC are reported as approximations
λ_z	Apparent terminal elimination rate constant, determined by linear regression using the terminal log-linear phase of the log transformed concentration vs. time curve
$t_{1/2term}$	Apparent terminal elimination rate constant, determined by linear regression using the terminal log-linear phase of the log transformed concentration vs. time curve

$t_{1/2\text{eff}}$	Effective half-life
R_A	Accumulation Index
CL/F	Total apparent oral clearance
V_{ss}/F	Apparent oral volume of distribution at steady state

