14.8. Efficacy Analyses

Patient listings will be provided for efficacy evaluations including PSA response rate, time to PSA progression, and rPFS.

Post-treatment percent change in PSA relative to baseline will be reported at Week 12 (or earlier for those who discontinue therapy), and separately, the maximal change at any time on study will also be reported for each patient and summarized using waterfall plots.

For Part 2, efficacy summaries by population cohort will be performed. Median time to PSA progression will be determined separately for each of the expansion cohorts and Kaplan-Meier curves may be plotted. If there is sufficient data, rPFS will be summarized and median rPFS will be assessed. If deemed appropriate, patients receiving the same dose from Part 1 may also be combined with Part 2 patients.

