Nodal	Previously normal (<1.0 cm) lymph nodes must have grown by ≥ 5 mm in the short axis from baseline or nadir and be ≥ 1.0 cm in the short axis to be considered to have progressed
	Nodes that have progressed to 1.0 to less than 1.5 cm are pathologic, subject to clinical discretion, and nonmeasurable
	For existing pathologic adenopathy (≥ 1.5 cm), progression is defined per RECIST 1.1
Bone Metastatic	
Endpoints for control/relief/elimination	Record changes as improved or stable (no new lesions) or worse (new lesions) or resolved bone lesion
	Changes in intensity of uptake alone do not constitute progression or regression
	No new lesions: continue therapy in absence of other signs of progression

Endpoints for delay/prevention/progression	Exclude pseudoprogression in the absence of symptoms or other signs of progression
	At least two new lesions on first post-treatment scan, with at least two additional lesions on the next scan (2+2 rule) If at least two additional new lesions are seen on the next (confirmatory) scan, the date of progression is the date of the first post-treatment scan, when the first two new lesions were documented
	For scans after the first post-treatment scan, at least two new lesions relative to the first post-treatment scan confirmed on a subsequent scan
	Date of progression is the date of the scan that first documents the second lesion

Abbreviations: CNS = central nervous system; CRPC = castration-resistant prostate cancer; RECIST = Response Evaluation Criteria in Solid Tumors.

Source: Scher HI, Morris MJ, Stadler WM et al. Trial design and objectives for castration-resistant prostate cancer: updated recommendations from the Prostate Cancer Clinical Trials Working Group 3. J Clin Oncol. 2016; 34(12):1402-1418. [8]

**APPENDIX 4. NATIONAL CANCER INSTITUTE (NCI) COMMON
TERMINOLOGY CRITERIA FOR ADVERSE EVENTS
(CTCAE)**

The NCI CTCAE (Version 4.03) should be used to assess Adverse Events and may be reviewed on-line at the following NCI website:

https://evs.nci.nih.gov/ftp1/CTCAE/CTCAE_4.03_2010-06-14_QuickReference_8.5x11.pdf

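### The Section 14.1 efficacy set makes the Week 12 PSA response denominator depend on an undefined on-study assessment, which can only raise the rate or leave it unchanged

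*Combined protocol and SAP*

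**What the plan says.** Section 4.1 lists PSA response at Week 12 as the only efficacy item among the primary endpoints. Section 5.1.2 plans three single-arm cohorts of up to 15, 30 and 15 patients. Section 14 makes the analysis descriptive, with no hypothesis test, and leaves details to a SAP.

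The text that bears on the denominator is this:

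- **Section 14.1, efficacy set:** "This population includes all patients who received at least 1 dose of study drug and underwent a relevant efficacy assessment". No type or timing of assessment is given. The PK set in the same section has a countable minimum: patients must "have at least 1 post dose concentration measurement of TRC253".
- **Section 14.2:** the worked example uses everyone: "If the total of 30 patients from this example, if 15 are PSA responders", the rate is 50% with a 95% interval of 31.3% to 68.7%.
- **Section 14.3:** response is a fall of 50% or more from baseline, with confirmation: "An additional PSA obtained at least 4 weeks later must show" the same fall. Censoring rules are given for time to PSA progression and for rPFS. The binary endpoint has no rule for a missing Week 12 value.
- **Section 14.8:** "Post-treatment percent change in PSA relative to baseline will be reported at Week 12 (or earlier for those who discontinue therapy". This section names no analysis set for the response rate.
- **Table 8 and Section 6.1.5:** PSA is drawn on Day 1 of every cycle and at End of Treatment, 7 days (±2) after the last dose. Scans are at "C3, then every 3 cycles: C6, C9, etc".

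**The concern.** In a single-arm cohort the response rate and its interval are the whole efficacy result, so it matters who is in the denominator. The one efficacy population in the plan requires something to have happened after enrolment, and the reader cannot tell what.

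Under the Section 14.3 definition, a treated patient with no Week 12 PSA adds nothing to the numerator. The numerator is therefore settled and only the denominator is open. Every way of using the condition to remove such a patient pushes the rate in one direction, upwards, unless there are no responders. The study is open-label, so if the meaning of the condition is settled late, it may be settled by people who already know the outcomes.

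**Working it through.** **1. Reproduce the plan's figure.** Inputs from Section 14.2: n = 30, x = 15. The Clopper-Pearson 95% interval for 15/30 is 31.3% to 68.7%, as stated. The Wald interval would be 32.1% to 67.9%, so the plan used the exact method, with all 30 patients as denominator.

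**2. Direction.** Let x be responders, n treated patients, and k excluded patients, none of them a responder. The change in the rate is

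x/(n − k) − x/n = xk / [n(n − k)] ≥ 0,

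and the rate is multiplied by n/(n − k).

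**3. Timing in Part 2 (28-day cycles, Table 8).** Cycle 4 Day 1 is day 1 + 3 × 28 = 85, which is the Week 12 PSA. With the ±2-day visit window this is days 83 to 87. The End of Treatment PSA falls 5 to 9 days after the last dose. It can land on days 83 to 87 when the last dose is between day 83 − 9 = 74 and day 87 − 5 = 82. Using the visit window as the Week 12 analysis window is my assumption; the plan defines no analysis window.

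**4. Two readings of the condition.**

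- *(a) Any post-baseline PSA or scan qualifies.* A patient who stops early but attends End of Treatment has a PSA. Exclusion is then largely confined to those who miss that visit too and had no earlier post-baseline PSA or scan. This should be few patients.
- *(b) A Week 12 PSA is required.* Most patients who stop before about Week 12 are excluded, apart from those whose End of Treatment PSA falls in the window in step 3.

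**5. Size.** The documents give no rate of stopping before Week 12. Section 2.4 reports three discontinuations for adverse events but not when they occurred. The values of k below are therefore assumptions, as is x = 5 for a 15-patient cohort.

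| Treated | Responders | Excluded k | Multiplier | Rate | 95% exact interval |
|---|---|---|---|---|---|
| 30 | 15 | 0 | 1.000 | 50.0% | 31.3-68.7 |
| 30 | 15 | 1 | 30/29 = 1.034 | 51.7% | 32.5-70.6 |
| 30 | 15 | 2 | 30/28 = 1.071 | 53.6% | 33.9-72.5 |
| 30 | 15 | 3 | 30/27 = 1.111 | 55.6% | 35.3-74.5 |
| 15 | 5 | 0 | 1.000 | 33.3% | 11.8-61.6 |
| 15 | 5 | 1 | 15/14 = 1.071 | 35.7% | 12.8-64.9 |
| 15 | 5 | 2 | 15/13 = 1.154 | 38.5% | 13.9-68.4 |

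In the 30-patient example the shift is 1.7 to 5.6 percentage points. The half-width of the plan's own interval is (68.7 − 31.3)/2 = 18.7 points.

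**The case against.** **A rule may exist elsewhere.** Section 14 calls itself a general description and defers details to a SAP. This stands in part. The supplied text contains no separate SAP rule, so one can neither be assumed nor ruled out. A reader might infer that the sponsor has no rule at all, and the documents do not support that. Even so, Section 14.1 as written does state a condition that removes treated patients.

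**The plan appears to keep early leavers.** Section 14.8 reports an earlier value for those who discontinue, and response is a threshold on the same percent change. This makes reading (b) less natural but does not exclude it. The wording governs the percent-change report and says nothing about responder status or the denominator. It also does not cover a patient still on treatment who misses the visit. The 15-of-30 example points the same way, but it is an illustration and not a rule.

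**Few patients are at risk.** The End of Treatment PSA supports this under reading (a), and it stands. It also means that the tempting statement that everyone who leaves before day 85 is lost under reading (b) goes too far (step 3).

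**Early progressors.** A reader might infer that the set systematically drops patients who progress early. The documents do not settle this. Bone progression found on the first post-treatment scan needs confirmation on the next scan (Appendix 3), which Table 8 schedules at Cycle 6 (day 141), after Week 12. Section 7.4.2, however, lets the investigator stop treatment for progression without naming that confirmation. Section 7.4.3 item 4a pulls the other way: "Patients may continue on study drug if in the opinion of the Investigator, patient is deriving benefit from continuation of therapy", subject to sponsor approval.

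**The effect is small and visible.** There is no test or threshold, the intervals overlap heavily, and the patient listings in Section 14.8 should let a reader see missing cases. All of this stands, and it limits the point to a cheap improvement.

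**Conclusion.** The point holds in a limited form. Section 14.1 makes the denominator of the primary PSA response rate conditional on an unspecified on-study assessment, and excluding patients with no Week 12 PSA can only raise the rate or leave it unchanged. The text permits this. It does not show that it will happen, and the size cannot be derived from the documents.

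The conclusion rests on two things: that the Section 14.1 efficacy set is the denominator for PSA response, since no other efficacy population is defined, and that Section 14.3 requires a Week 12 value for response. A missing confirmatory PSA is outside the point, because Section 14.3 most naturally makes it a non-response.

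Larger shifts are arithmetically possible. With 6 of 30 excluded, 15/24 = 62.5% (40.6-81.2). That needs 20% of patients to be missing, and nothing in the documents supports such a figure. What is affected is a descriptive rate and its interval; no error rate or decision rule changes.

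**What to change.** In Sections 14.1 and 14.8:

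1. Make the denominator for the primary PSA response rate all patients in each Part 2 cohort who received at least one dose, as the example in Section 14.2 already does.
2. Count a missing Week 12 PSA as non-response.
3. State that the earlier value allowed in Section 14.8 for patients who discontinue serves the percent-change report only.
4. Report the rate among assessed patients as a sensitivity analysis, with *assessed* defined (which measurement, in which window) and the excluded patients listed with reasons.

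If a SAP already contains such a rule, cite it in Section 14.1. The change is wording only and uses data already collected. Its one cost is that the reported rate may be slightly lower than under an assessed-only denominator.

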14.2. Sample Size Determination

The sample size for this study is not calculated based on statistical power but to obtain safety, PK, and PD assessments of oral doses of TRC253. In Part 1, dose escalation, patients up to six patients per dose level will be enrolled to evaluate for DLT. In Part 2, dose expansion, approximately 60 patients will be enrolled into three separate cohorts for further safety and PK evaluation. For example, if true PSA response rate is 50%, the probability of observing at least 11 responders out of 30 in cohort 2 is 95%. If the total of 30 patients from this example, if 15 are PSA responders, then response rate (95% CI) will be 50% (31.3%, 68.7%).

14.3. Endpoint Definitions

PSA Response at Week 12

PSA response is defined as a $\geq 50\%$ decline from baseline according to PCWG3 criteria ([Appendix 2](#)). An additional PSA obtained at least 4 weeks later must show $\geq 50\%$ decline from baseline to confirm the response.

Time to PSA Progression

Time to PSA progression is measured from the start of treatment until the criteria for PSA progression according to the PCWG3 are met ([Appendix 2](#)). Patient without PSA progression will be censored at the last PSA assessment.

Radiographic Progression-Free Survival (rPFS)

Radiographic Progression-Free Survival (rPFS) is measured from the start of the treatment until the criteria for radiographic disease progression are met or death occurs, whichever is first. Patient will be censored at the last disease assessment when no rPFS event is observed.

Pharmacokinetic Parameters

Pharmacokinetic parameters of TRC253 will be derived from plasma concentration versus time data after single dose and repeat dose, as applicable. The pharmacokinetic parameters to be assessed are shown below. Other parameters may also be assessed.

C_{max}	Maximum observed plasma concentration for each patient
C_{min}	Observed plasma concentration at the end of dosing interval for each patient
t_{max}	Time of maximum observed plasma concentration
AUC_{τ}	Area under the plasma concentration-time curve from time zero to 24 hours (dosing interval) at steady state
AUC_{last}	Area under the plasma concentration-time curve from time zero to the last time measured
AUC_{∞}	Area under the plasma concentration-time curve from time zero extrapolated to infinite time calculated as $AUC_{last} + C_{last}/\lambda_z$, where C_{last} is the last observed measurable (non-BQL) concentration; extrapolations of more than 20.00% of the total AUC are reported as approximations
λ_z	Apparent terminal elimination rate constant, determined by linear regression using the terminal log-linear phase of the log transformed concentration vs. time curve
$t_{1/2term}$	Apparent terminal elimination rate constant, determined by linear regression using the terminal log-linear phase of the log transformed concentration vs. time curve

$t_{1/2\text{eff}}$	Effective half-life
R_A	Accumulation Index
CL/F	Total apparent oral clearance
V_{ss}/F	Apparent oral volume of distribution at steady state

The following requirements should be met for an acceptable calculation of $t_{1/2\text{term}}$, λ_z , AUC_∞ , and related parameters:

- A) at least 3 data points are used in the calculation, otherwise $t_{1/2\text{term}}$, λ_z , AUC_∞ , and related parameters are not assessable;
- B) coefficient of determination (r^2_{adj}) is at least 0.90.

If requirement (B) is not met, $t_{1/2\text{term}}$, λ_z , AUC_∞ , and related parameters will be reported as approximations.

Actual sampling times will be checked for major aberrations. In case a major aberration occurs for an actual sampling time of >20% deviation from the scheduled time (relative to study drug intake), this plasma concentration will be excluded from descriptive statistics in the plasma concentration table.

